I am submitting an annual continuation without modifications

Division & Personnel

Division

What Division/Department does the PI belong to?

Psychiatry

Within the division/department, what Center or group are you affiliated with, if any? program on healthy aging and late life brain disorders

Unaffiliated Personnel

List investigators, if any, who will be participating in this protocol but are not affiliated with New York State Psychiatric Institute or Columbia University. Provide: Full Name, Degrees and Affiliation.

[name] (SUNY Stony Brook)

[name] (SUNY Stony Brook)

Application for Continuation of Research

Status

Current Status of Study:

All research interventions were completed. Only data analysis is ongoing.

Summary of Experiences to Date

Please provide a summary of scientific progress of the study and the experience of research participants, to date. This requirement is designed to allow for the investigator and the IRB to reassess the study's risks and benefits in terms of developments in the field, changing practice patterns, and new IRB policies and procedures.

36 subjects participated who were 75.3 ± 7.5 years old and 44.4% male. Significant, dose dependent increases in processing and gait speed were observed with L-DOPA (450mg dose: processing speed factor score effect size [ES] = 0.41, p = 0.001; dual task gait speed ES = 0.43, p = 0.003). [11C]raclopride Δ BPND was significantly different from 0 in sensorimotor (t = -4.85, df = 24, p < 0.001) and associative striatum (t = -2.52, df 24, p = 0.019) but not in limbic striatum (t = 0.265, df = 24, p = 0.793). Depressive symptoms decreased significantly on the Hamilton Rating Scale for Depression (ES = -0.4, p = 0.01). Drop-out rate was 8.3%, and nausea was the most frequently-reported side effect. By enhancing availability of dopamine, L-DOPA improved processing and gait speed in depressed older adults and significantly decreased [11C]raclopride binding in selected striatal subregions.

Funding

Have there been any changes in funding status since the prior approval?

No

Have the principal investigator and other investigators made all required disclosures of financial interest in the study sponsor/product?

Yes

Summary

Have there been any study findings, recent literature, or untoward events occurring here or at other sites in the past year which might affect the analysis of the safety, risks or benefits of study participation? No

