- 16. Drs. [name] and [name] continue to be Co-Investigators responsible for neuroimaging as part of a subcontract executed between RFMH and SUNY-Stony Brook. They will lead analyses of neuroimaging data. In terms of on-site execution of PET and MRI scans, these are supervised by the study PI ([name]) and/or [name], who works with the Aging Program as a study clinician and has a research background in PET neuroimaging.

Clinical treatment

- 16. An effort will be made for all subjects to be titrated up to 450mg L-DOPA over a 3 week-duration study. We chose 450mg as the target dose because it is higher than doses known to affect cognition (i.e., 150-300mg) but lower than levels used for PD (i.e., 600-1200mg) that may have greater side effects. Each subject will start taking 37.5mg carbidopa/150 mg levodopa (1.5 25/100 sinemet tablets) once daily for one week, then increase to 75mg carbidopa/300mg levodopa (1.5 25/100 sinemet tablets twice daily) for one week, and finally increase to 112.5mg carbidopa/450mg levodopa (1.5 25/100 sinemet tablets three times daily) for one week. Each subject will be titrated to 450mg L-DOPA unless they cannot tolerate higher doses, in which case subjects will have their dosage reduced to the maximum tolerable dose.
- 17. Although each subject is titrated up to 450mg L-DOPA if it is tolerated, the study design allows us to assess the effects and tolerability of three different L-DOPA doses (150mg, 300mg, and 450mg). Based on published work using L-DOPA for PD, we expect effects on cognition and gait to be apparent at each dosing level approximately 5 days after dosage increases. By performing assessments weekly, we will thus obtain measures of L-DOPA's effect on processing and gait speed at each dosing level. We carefully reviewed the literature and consulted our Co-Investigator [name] (neurologist and PD expert) for evidence of carry-over effects of L-DOPA dosing (such that prior experience with 150mg and 300mg may influence a subject's experience of receiving 450mg). We found little evidence to suggest there are significant carry-over effects from previous L-DOPA doses, so each dose will be able to be assessed on its own merits. Similarly, we do not anticipate that the repeated assessments of processing and gait speeds will bias the study results.

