- 18. In selecting L-DOPA doses, we balanced appropriate safety concerns regarding the use of this medication in a novel patient population with the goal of causing a measurable effect. L-DOPA is an extremely well tolerated medication at doses < 600mg, which is substantially less than the doses often reached in the treatment of Parkinson's disease (900-1200mg). L-DOPA has been administered to healthy subjects in single dose studies and found to be well-tolerated. In Parkinson's disease, a recent clinical trial published in the New England Journal of Medicine randomized patients to receive 150mg, 300mg, or 600mg L-DOPA for 40 weeks. In the 150mg and 300mg L-DOPA treatment groups, the only side effects

observed that were different from placebo were headache and nausea. No dyskinesias or other neuropsychiatric effects were observed that were greater than the placebo group. In terms of effects, single-dose studies have reported significant effects on cognition and neural activation with L-DOPA doses as low as 100mg. Thus, we believe the 150-450mg dose range to be used in this study will be both safe and likely to produce an observable effect.

Assessments

- 19. Subjects are expected to have a screening/evaluation visit, PET/MRI scanning day (for those receiving imaging), and weekly visits from Week 0-3.
- 20. At baseline, we will record each subject's chief complaint, referral source, age of onset of mood and/or cognitive decline, number prior depressive episodes, age, sex, marital status, race and ethnicity, years of education, employment status and income, years of education, family history. We also will document medical history, physical exam, urine drug screen, CBC, chemistries and electrolytes, thyroid profile, vitamin B12 and folate levels, urine analysis, and ECG. Vital signs will be measured at baseline and monitored weekly throughout the study. The Cumulative Illness Rating Scale-Geriatric (CIRS-G) (112) will be filled out at baseline to measure chronic medical illness burden. Subjects' current physical pain will be assessed weekly using a 100mm Pain Visual Analog Scale (VAS) and used as a covariate in analyses of gait speed (113).

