- 21. The following measures will be collected weekly throughout the study: 24-item HRSD, CGI Severity and Improvement, Structured Pill Count Interview, Unified Parkinson's Disease Rating Scale (UPDRS) (questions 32 and 33 will be used in this study to assess the duration and disability of dyskinesias caused by L-DOPA), Treatment Emergent Side Effect Scale, and Inventory of Depressive Symptoms—Self Report (IDS-SR).
- 22. In addition, processing and gait speed assessments will be performed weekly at 1pm to control for time of day effects and the duration since the last morning L-DOPA dose (anticipated to be 4 hours). Processing speed will be assessed using the Digit Symbol test from the Wechsler Adult Intelligence Scale-III (WAIS-III) (119) and the Pattern and Letter Comparison tests (120). These tests are all reliable and valid, with moderate to high loadings on the latent speed factor. A latent factor (and subsequent factor score) will be extracted from the 3-test battery pre- and post-treatment and used as the main outcome in the R61. By extracting a latent factor and factor loadings we will utilize a more pure measure of processing speed than if we used the raw scores from an individual test or a sum total score from the three raw scores combined (121-124).
- 23. Gait will be assessed as both a single and dual task (ST, DT) on a 15' walking course in the LLDC. For the ST, patients are instructed to walk at their usual or normal speed over the 15' walking course. For the DT, patients are instructed to walk at their usual pace while simultaneously verbally listing as many animals as possible (fluency DT). In addition, a counting DT will be used in which patients are instructed to walk at their usual pace while simultaneously performing serial subtractions by threes starting at 100 (125). Patients will start and end at a point 2 meters from beginning of the 15' course to eliminate acceleration and deceleration effects. Each ST and DT will be assessed two times with the average used in the analyses. The ST assessment of walking speed in m/s will be used as the primary outcome measure for this study.

End of study procedures

24. Following the 3 week duration treatment study, endpoint assessments will be made. Patients will enter 3 month open treatment period provided free of charge as described below.

You can upload charts or diagrams if any

Criteria for Early Discontinuation

Criteria for Early Discontinuation

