Descriptive statistics are expressed as means and standard deviations or percentages. Chi-square analyses and independent samples t-tests were used to analyze dose dependent increases in processing and gait speed. Also the changes in Hamilton Rating Scale for Depression.

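### The SAP names independent-samples t-tests for repeated weekly scores from one group of subjects; it should name a within-subject analysis that can carry the promised pain covariate

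*Combined protocol and SAP*

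**What the plan says.** The Statistical Analysis plan is three sentences at the end of the combined document. After a line on descriptive statistics it says: "Chi-square analyses and independent samples t-tests were used to analyze dose dependent increases in processing and gait speed". A fragment follows: "Also the changes in Hamilton Rating Scale for Depression". No paired test, mixed model or analysis of covariance is named anywhere in the document.

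The design is under Study Procedures. Clinical treatment, item 16 (the second item so numbered), steps the dose up weekly: "Each subject will be titrated to 450mg L-DOPA unless they cannot tolerate higher doses". Item 17 explains that weekly testing is meant to measure the drug's "effect on processing and gait speed at each dosing level". There is no comparison group.

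Under Assessments, item 20 has pain rated weekly "and used as a covariate in analyses of gait speed". Item 22 describes a processing-speed factor score "used as the main outcome in the R61". Item 23 says: "The ST assessment of walking speed in m/s will be used as the primary outcome measure for this study", where ST is the single-task walk; dual-task walks are also timed.

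The Summary of Experiences to Date gives 36 participants, drop-out of 8.3% and, at 450 mg, "processing speed factor score effect size [ES] = 0.41, p = 0.001; dual task gait speed ES = 0.43, p = 0.003". For HRSD it gives an effect size of -0.4 with p = 0.01.

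**The concern.** The 150, 300 and 450 mg scores come from the same people one week apart. An independent-samples t-test treats each visit as a different group. When a person's scores are positively correlated, the variance of the change is smaller than that test assumes, so its standard errors are too large and power is lost. The error is in the conservative direction.

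The test also has no term for a covariate, so the SAP and the pain adjustment promised for gait in Assessments, item 20, cannot both be followed.

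What is at stake is whether a reader can trace the reported results to the stated plan. The SAP is the only description of the behavioural and mood analysis in the document, and applying it to the reported effect sizes gives p-values far from those reported.

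**Working it through.** **Inputs from the document.** N = 36; drop-out 8.3%, which fits 3/36 = 0.083 and so about 33 subjects at Week 3; effect sizes (ES) 0.41, 0.43 and -0.4 with p = 0.001, 0.003 and 0.01.

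**Assumptions, not in the document.** ES is the mean change divided by the SD of the score, with equal SDs at both visits. The number of subjects per visit is 33 to 36. Tests are two-sided at 0.05 unless stated.

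**Step 1: the test the SAP names.** t = ES / sqrt(1/n1 + 1/n2), df = n1 + n2 - 2. For processing speed with 36 at each visit, t = 0.41 / 0.2357 = 1.74 on 70 df, p = 0.086.

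| Outcome | 36 and 36 | 36 and 33 | 33 and 33 | Reported |
|---|---|---|---|---|
| Processing speed, 0.41 | 0.086 | 0.094 | 0.101 | 0.001 |
| Dual-task gait, 0.43 | 0.072 | 0.079 | 0.086 | 0.003 |
| HRSD, 0.40 in size | 0.094 | 0.102 | 0.109 | 0.01 |

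One-sided values are half of these, 0.036 to 0.055. Two-sided p < 0.05 would need an ES of 0.470 (36 per visit) to 0.492 (33 per visit). Rounding does not close the gap: HRSD at 0.45 with 36 per visit still gives p = 0.060.

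A further check: at similar n, an independent test must give the larger effect the smaller p. Here 0.43 carries p = 0.003 and 0.41 carries p = 0.001.

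**Step 2: a paired test.** The SD of change, in score-SD units, is sqrt(2(1 - r)), where r is the baseline-to-Week-3 correlation, and t = ES x sqrt(n) / SD of change on n - 1 df. Solving for r at the reported p: SD of change = ES x sqrt(n) / t(p), then r = 1 - SD²/2. For processing speed with n = 36, t(p) = 3.591, SD = 0.41 x 6 / 3.591 = 0.685, r = 1 - 0.469/2 = 0.765.

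| Outcome | r needed, n = 36 | r needed, n = 33 |
|---|---|---|
| Processing speed | 0.765 | 0.789 |
| Dual-task gait | 0.673 | 0.704 |
| HRSD | 0.612 | 0.648 |

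These are plausible for the same measure three weeks apart. If ES were instead already divided by the SD of change, a paired test would give 0.019-0.025, 0.014-0.019 and 0.022-0.028, which does not match either.

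**Step 3: power at ES 0.41, n = 33.** By its own formula the independent test has 0.375. The paired test has 0.627, 0.838 and 0.951 at r = 0.5, 0.7 and 0.8.

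**Step 4: the imaging results.** The raclopride tests in the same summary have 24 df and test change against zero. They reproduce as one-sample tests on 25 subjects (t = -2.52 gives 0.0188; t = 0.265 gives 0.793). Two independent groups of 25 would have 48 df. So a within-subject test was used there, although the SAP does not mention it.

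**The case against.** The strongest reply is that this is a slip in a three-sentence, past-tense description, and that the right analysis was probably run. That is likely true, and it means the fix may be wording only. It does not remove the mismatch between the stated test and the design.

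A second reply is that the p-value comparison rests on an undefined effect size and unstated sidedness. This stands in part. One-sided, the independent test falls below 0.05 in most cases, so it cannot be said without conditions that no effect would be significant. But 0.036-0.055 is still far from 0.001-0.01. Likewise, the paired match solves one correlation for each p-value, so it shows plausibility and is not proof.

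Readers might infer several stronger points that the documents do not support:

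- **That the reported effects are false.** The named test errs towards non-significance, and a within-subject analysis fits the reported values.
- **That the decision to proceed to the R33 phase was wrong.** Specific Aims and Hypotheses refers to thresholds, but they are not given, so nothing ties the decision to these p-values.
- **That the summary reports dual-task gait and not single-task because of the t-test.** That is a separate reporting matter, as are the withdrawal rules.
- **That drop-out hardly matters.** Adding three subjects to 33 completers in the paired calculation, p passes 0.05 only if they worsened by about 1.3 SD for processing speed and 1.2 SD for dual-task gait, but for HRSD about 0.85 SD is enough.

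**Conclusion.** The point holds in a narrow form. The SAP names a test that does not suit a single-arm, repeated-measures design and cannot carry the pain covariate the protocol promises. Neither statement needs any assumption beyond positive within-person correlation.

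The cost, if the named test were really used, is roughly a fall in nominal power from 84% to 38% at effect 0.41, 33 subjects and correlation 0.7. The failure to reproduce the reported p-values depends on reading effect sizes in SD-of-score units; the statement that all three exceed 0.05 also needs two-sided testing. The likeliest explanation is a misdescribed analysis. This is a worthwhile correction to the plan and does not count against the findings.

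**What to change.** Replace the t-test sentence and the HRSD fragment with a repeated-measures mixed model of Weeks 0-3:

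- Visit (scheduled dose level) as the within-subject factor, unstructured covariance, and every available visit from all treated subjects, so that Weeks 1-2 still contribute when Week 3 is missing.
- Week 3 minus Week 0 as the contrast for 450 mg.
- Outcomes: processing-speed factor score, single-task gait, dual-task gait and HRSD.
- For gait, weekly pain as a covariate, repeated without it because pain measured on drug may itself change.
- A statement that week and dose cannot be separated under forced titration.

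Paired tests are the minimum acceptable substitute, but they leave out the pain covariate and the partial follow-up. If a drop-out sensitivity analysis is reported, include HRSD.

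If a within-subject analysis was already run, correct the SAP to name it; the cost is the wording. If not, label the new model post hoc, because results have been reported; the cost is one SAP paragraph and one model for each of four outcomes. Interventions are complete and analysis is continuing, so no new visits or subjects are needed.
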